12.3 Subject Withdrawal Criteria

Once a subject starts study treatment, any subject not completing the study for any reason will be considered a premature termination and the Investigator must record the reason(s) for withdrawal in the subject's source document and electronic case report form (eCRF). Any subject that discontinues prematurely, regardless of the reason, will be requested to complete all early discontinuation assessments and procedures (see Section 14.7). Once withdrawn, subjects may not re-enter the study, nor will they be replaced.

Subjects are free to discontinue their participation in the study at any time and without prejudice to further treatment. In such cases, the subject/caregiver will be queried as to the reason(s) for the decision to withdraw consent and the reasons(s) clearly documented in the subject's source document and eCRF to ensure the decision was not due to an adverse event (if due to an adverse event, the adverse event should be indicated as the reason for discontinuation even if the Investigator would not have considered discontinuation of treatment because of the adverse event).

The Investigator or Sponsor may discontinue individual subjects from the study at any time if it is deemed clinically appropriate or for any reason, including the following:

- An intolerable adverse event or serious adverse event (SAE);
- Insufficient therapeutic response, including:
 - Lack of effectiveness – no improvement in USFR or CGI-C after the subject’s initial treatment when comparing scores at Week 4 versus respective scores at baseline (Day 1);
 - Loss of effectiveness – after demonstrating some improvement in USFR and CGI-C scores post-injection on the subject’s initial treatment, 1 or both of these assessments is not improved on subsequent injections at Week 4 versus the respective score at baseline (Day 1);
- Requires a medication that was prohibited (see Sections 11.1.2 and 16.10) by the protocol;
- Does not follow guidelines specified in the protocol;
- Is lost to follow up; and
- In the Investigator’s opinion, does not continue to meet entry criteria.

The clinical course of each adverse event should be followed until resolution, stabilization, or until it has been determined that the study treatment or participation is not the cause. Serious adverse events that are still ongoing at the end of the study period must be followed up to determine the final outcome (see Section 16.2.7).

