Subjects prematurely discontinuing due to lack of effectiveness or loss of effectiveness will be encouraged to return to the study site to complete early termination study procedures to evaluate safety and saliva production.

In cases where a subject fails to return for required visits, repeated attempts will be made to reach the subject/caregiver

If repeated attempts are unsuccessful, lost to follow up will be recorded in the subject’s source document and eCRF as the reason for early termination.

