14.7 Early Discontinuation

If the subject is withdrawn from the study before completion of the study, the reason for withdrawal from the study must be documented in the subject's source document and eCRF. Whenever a subject withdraws, the procedures/assessments listed below should be conducted.

- Evaluation of adverse events;
- Complete physical exam (including vital signs and weight);
- FVC (as clinically warranted);
- Clinical laboratory tests (fasting), including full chemistry panel (including glucose and alkaline phosphatase), hematology, and urinalysis;
- Urine pregnancy test;
- Neurologic exam;
- Dental exam by a licensed dentist (including 4 bite-wing radiographs or panoramic imaging [if edentulous or if bite-wing x-rays are difficult due to limited teeth]);
- C-SSRS Since Last Visit version;
- Review of concomitant medications;
- Review of subject diary;
- CGI-S and CGI-C (Assessor) before USFR;
- USFR collection;
- DFSS-I;
- PGI-S and PGI-C (Subject);
- DIS (Subject); and
- DFSS-S via entry in subject's diary, not during study visit.

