2.6.2 Safety measures

Adverse events are recorded at each study visit, starting from the first injection of MYOBLOC on Day 1 of Treatment Session 1 and ending at study completion (i.e., 52 ± 1 week). Subjects who discontinue because of an adverse event before study completion will be contacted 13 weeks (±3 days) after their last injection of study drug to assess the adverse event. Serious adverse events, adverse events of special interest, and other immediately reportable adverse events were collected during the study period (or within 13 weeks ±3 days of last study drug injection for subjects discontinuing participation prematurely). Dental and oral health are followed closely throughout the course of the study by monitoring dental adverse events (DAE), as defined in the study protocol.

Vital signs (blood pressure, pulse, respiratory rate, and temperature) are measured after sitting quietly for at least 5 minutes at screening and each study visit, if applicable, at early termination from the study.

Subjects' suicidal ideation and behavior are measured at each study visit (including Day 1 and Weeks 4, 8, 13, 17, 26, 30, 39, 43, and 52) or, if applicable, early termination from the study, using the Columbia Suicidal Severity Rating Scale (C-SSRS). The C-SSRS baseline version (Appendix I of the protocol) will be used for Day 1, whereas the C-SSRS since last visit version (Appendix J of the protocol) will be used for all of the other visits. The C-SSRS has three subscales: suicidal ideation (Categories 1-5), suicidal behavior (Categories 6-10), and intensity of suicidal ideation. Both suicidal ideation subscale and suicidal behavior subscale have 5 yes-no categories each, with a sum score ranging from 0 to 5 and higher score indicating greater severity.

Category 1 – Wish to be Dead

Category 2 – Non-specific Active Suicidal Thoughts

Category 3 – Active Suicidal Ideation with Any Methods (Not Plan) without Intent to Act

Category 4 – Active Suicidal Ideation with Some Intent to Act, without Specific Plan

Category 5 – Active Suicidal Ideation with Specific Plan and Intent

- Category 6 – Actual Attempt
- Category 7 – Interrupted Attempt
- Category 8 – Aborted Attempt
- Category 9 – Preparatory Acts or Behavior
- Category 10 – Suicidal Behavior

The intensity of suicidal ideation has 5 items (2 are scored from 1 through 5 and the other three from 0 to 5), with a sum score ranging from 2 to 25 where higher score indicate greater risk.

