Withdrawals due to adverse events will be summarized for each body system and preferred term. Serious adverse events (SAEs) (including deaths) will be listed for individual events.

Narratives will be provided for all deaths, non-fatal serious adverse events, and subjects withdrawn due to adverse events.

Vital Signs and Weight

Vital signs and weight will be summarized descriptively by treatment session at pre-injection (i.e., Day 1 and Weeks 13, 26, and 39) and at each post-injection time point of 4 weeks post-injection (i.e., Weeks 4, 17, 30, and 43), 8 weeks post-injection (i.e., Week 8 first treatment session only), and 13 weeks post-injection (i.e., Weeks 13, 26, 39, and 52). The change scores in vital signs and weight from baseline at 4 weeks, 8 weeks (first treatment session only), and 13 weeks post-injection will be summarized descriptively.

Neurologic Exam

Abnormal findings of neurological exam data will be listed, respectively, for individual subjects.

Lung Functioning Test

Findings of forced vital capacity (FVC) data will be listed, respectively, for individual subjects.

Physical Examination

A complete Physical Examination was performed at Screening, Week 4, Week 13, Week 26, Week 39, Week 52, and Early Discontinuation. A brief Physical Examination was performed at Day 1, Week 8, Week 17, Week 30, and Week 43 when body weight, height and body mass index (BMI) were recorded. If any of the Physical Examination findings were abnormal and clinically significant prior to treatment, the event was recorded as medical history, while if occurred after treatment the event was recorded as a TEAE.

Suicidality Assessment

For each treatment session, each of the three C-SSRS subscales (suicidal ideation, suicidal behavior, and intensity of suicidal ideation) will be summarized descriptively for continuous variable at each pre-injection visit (i.e., Day 1 and Weeks 13, 26, and 39) and at each post-injection time point of 4 weeks post-injection (i.e., Weeks 4, 17, 30, and 43), 8 weeks post-injection (i.e., Week 8, first treatment session only), and 13 weeks post-injection (i.e., Weeks 13, 26, 39, and 52). The change scores in C-SSRS subscales from pre-injection at 4 weeks, 8 weeks (first treatment session only), and 13 weeks post-injection will be summarized descriptively.

Dental Examination and Oral Examination

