5.11 Clinical Laboratory Evaluation

For the safety population, descriptive statistics of clinical laboratory tests will be presented at screening and end of treatment session respectively, for hematology, chemistry, and urinalysis (specific gravity and pH) for Treatment Session 1, Treatment Session 2, Treatment Session 4 as well as End of Study. Qualitative findings in terms of abnormal low, normal, and abnormal high at screening and end of treatment session will be tabulated for hematology, chemistry, and urinalysis, respectively, for Treatment Session 1, Treatment Session 2, Treatment Session 4 as well as End of Study.

Any clinically significant abnormalities (based upon laboratory ranges) observed during the study will be listed for hematology, chemistry, and urinalysis, as well as pregnancy test.

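### C-SSRS, weight and vital signs taken at the Early Discontinuation visit are listed but enter no summary table that the SAP text describes

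*SAP*

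**What the plan says.** **Collection.** Protocol 14.7 opens its list with: "Whenever a subject withdraws, the procedures/assessments listed below should be conducted". The list includes a complete physical exam with vital signs and weight, and the "C-SSRS Since Last Visit version". The Early Discontinuation column of Protocol Table 2, repeated in SAP Table B, marks all three measures. SAP 2.6.2 repeats that vital signs and C-SSRS are taken at early termination. Attendance is a request: under Protocol 12.3 a subject who stops early "will be requested to complete all early discontinuation assessments and procedures". Those who stop for lack or loss of effectiveness are encouraged to come back and "complete early termination study procedures to evaluate safety and saliva production".

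**Analysis.** SAP 2.9.2 summarises vital signs, weight and the three C-SSRS subscales at pre-injection (Day 1, Weeks 13, 26, 39), 4 weeks after injection (Weeks 4, 17, 30, 43), Week 8 in Session 1, and 13 weeks after injection (Weeks 13, 26, 39, 52). For C-SSRS change it names "The change scores in C-SSRS subscales from pre-injection at 4 weeks, 8 weeks (first treatment session only), and 13 weeks post-injection", and it uses the same points for change in vital signs and weight. SAP 5.7 and 5.12 refer to pre- and post-injection time points by session. Protocol 17.7 uses the same weeks.

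**Contrast.** Laboratory tests are summarised at whatever visits are available (SAP 2.9.2), and SAP 5.11 runs to "Treatment Session 4 as well as End of Study".

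**The concern.** The primary objective is long-term safety and tolerability, and C-SSRS is a listed safety endpoint. The discontinuation C-SSRS asks about the period since the last visit, so it is the only C-SSRS that covers the interval between a subject's last attended visit and departure. In Sessions 2 to 4 the clinic visits fall at 4 and 13 weeks after injection, which leaves a gap of 13 − 4 = 9 weeks. The telephone contact in that gap collects adverse events and medications, but no C-SSRS and no weight.

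If the discontinuation record has no place in the tables, the tabulated C-SSRS, weight and vital-sign values stop at each leaver's last scheduled visit. C-SSRS is the most exposed. It is summarised as a continuous score at each time point, with no count of subjects who ever report ideation or behavior, so a handful of positive responses at discontinuation would appear in no described table.

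**Working it through.** **Step 1: is the value collected, and is it tabulated?**

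| Measure | At Early Discontinuation | Summary points in SAP 2.9.2, 5.7, 5.12 | Early-termination or last-value row in the SAP text |
|---|---|---|---|
| C-SSRS | Yes (Protocol 14.7, Table 2; SAP 2.6.2, Table B) | Pre-injection; 4, 8 (Session 1) and 13 weeks | None |
| Weight | Yes (Protocol 14.7, Table 2; SAP Table B) | Same | None |
| Vital signs | Yes (Protocol 14.7, Table 2; SAP 2.6.2, Table B) | Same | None |
| Laboratory tests | Yes (Protocol 14.7, Table 2; SAP 2.6.2, Table B) | Available visits | End of Study (SAP 5.11) |

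SAP 5.11 does not say whether its End of Study results include discontinuation records. The contrast shows only that laboratory data have a possible home for them and the other three measures do not.

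**Step 2: does another section place the record?** SAP 2.8 covers missing values, partial dates and repeats, and sends all records to listings. It contains no visit-window rule. SAP 5.2 covers termination counts and details only. The text has no last-value summary and no any-post-injection summary.

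**Step 3: how many subjects?** The plan has no figure to reproduce. Inputs: N = 187 (SAP 2.5); dropout fraction d assumed at 10%, 20% and 30%. Affected subjects, at most = N × d:

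- 187 × 0.10 = 18.7, about 19
- 187 × 0.20 = 37.4, about 37
- 187 × 0.30 = 56.1, about 56

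These are upper bounds. A subject who is lost, dies or declines the visit has no record. A withdrawal that coincides with a scheduled visit may be tabulated there.

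**Step 4: would an unwritten window rule close the gap?** Take the protocol's visit windows at nominal weeks and count the days from 1 to 364 that they cover:

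- Weeks 4 and 8, ±3 days: 2 × 7 = 14
- Weeks 13, 26 and 39, ±14 days: 3 × 29 = 87
- Weeks 17, 30 and 43, ±5 days: 3 × 11 = 33
- Week 52, days 350 to 364: 15

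Total = 14 + 87 + 33 + 15 = 149, and 149/364 = 41%. If exit dates were uniform over the year (assumed), 59% of discontinuation visits would fall in no window: 18.7, 37.4 and 56.1 × 0.59 ≈ 11, 22 and 33 subjects. Exits that cluster at visits would lower this. Even inside a window, a discontinuation record mapped to a visit already attended would be a repeat, and SAP 2.8 analyses the first record.

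**The case against.** The strongest reply is that the important cases are already reported. Dysphagia is an adverse event of special interest, tabulated by session, and is also on the distant-spread list. Withdrawals due to adverse events are tabulated by body system and preferred term, and each gets a narrative. Clinically significant physical-exam findings after treatment become adverse events. By-visit summaries of observed values are a common choice in a descriptive single-arm study, and the shells could contain a row that the text omits.

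Most of this stands, and it narrows the point. A reader might infer that a subject who leaves because of dysphagia or a mood-related adverse event is invisible in the safety output. The documents do not support that: what goes untabulated is the numeric value and the scale response. The reply does not cover a subject who leaves for another reason, such as withdrawn consent or lack of effectiveness, and first gives a positive C-SSRS response at that visit. No withdrawal narrative is required for such a subject, and the supplied text does not say that a positive response must be recorded as an adverse event. An early-termination row in a shell cannot be excluded, but without SAP text its definition would remain open.

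Three other inferences also fail:

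- **That SAP 2.8 turns these records into missing data.** It applies to missing or invalid values, and it sends every record to listings.
- **That C-SSRS at discontinuation is itself a listed endpoint.** Protocol 9.1 lists C-SSRS at each study visit; the discontinuation wording belongs to the assessments (Protocol 16.9).
- **That mean weight change at study end is biased by some number of kilograms.** The SAP plans within-session changes from each pre-injection value, not a cumulative one, and the documents give no basis for a difference between leavers and stayers.

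**Conclusion.** The gap is real and modest. C-SSRS, weight and vital signs are requested at every withdrawal, and the SAP text puts them in listings but in no described summary table. With a dropout rate assumed between 10% and 30% of 187, at most about 19 to 56 subjects are affected. The direction and size of any effect on the tabulated means cannot be derived from the documents. The part that matters most is the absence of a count of subjects with any post-injection ideation or behavior. No test, sample size or significance level changes. The conclusion rests on the SAP text alone, because the table shells were not available.

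**What to change.** Amend SAP 2.9.2, 5.7 and 5.12 as follows.

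1. **C-SSRS:** add the number and percent of the safety population with any suicidal ideation, and with any suicidal behavior, at any post-injection assessment, including Early Discontinuation and unscheduled visits.
2. **Weight and vital signs:** add a row for the last on-study value (Week 52 or Early Discontinuation), with change from Day 1. State what is used for a subject who has neither record, since the protocol allows the study to stop before Session 4.

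The data are already on the schedule, so no visit or procedure changes. The cost is a few table rows and their programming. The timing of the last value will differ between subjects, so that row should stand apart from the fixed-week rows and show the number contributed by each source.

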2.9.3 Other analysis

Concomitant medications were grouped into those taken pre-enrollment and those taken post-enrollment, based upon the starting date of both the concomitant medication and the enrollment date. Number and percent of subjects who take concomitant medications were reported for each Treatment Session. Concomitant medications will be listed, respectively, for individual subjects.

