7. Anticipated or scheduled surgery during the study period. A PEG tube/G tube may be placed for nutritional support at any time during the study and will not exclude the subject from continued study participation.
8. Major surgery (requiring general anesthesia, except PEG tube/G-tube placement) within the previous 6 months before screening. If surgery occurred more recently than 6 months before screening, Investigator must have sufficient documentation to demonstrate the subject has fully recovered and stabilized. Prior movement disorder-related surgery (e.g., pallidotomy, thalamic/subthalamic/pallidal deep brain stimulation) will not exclude the subject, provided the surgery was performed at least 6 months before screening.
9. Anticholinergic and antihistamine medication eligibility restrictions (see also Section 16.10):
 - Oral/transdermal pharmacologic treatment (specifically antihistamines and those medications with anticholinergic properties) **for troublesome sialorrhea** must be discontinued during the 30-day period before screening and are not allowed in the entire duration of the study, except ALS subjects as allowed herein. For ALS subjects only: such medications for the treatment of sialorrhea are allowed; however, conversion to, or continuation of, a short-acting medication (duration of action of approximately 8 hours or less) is required at a stable dose/regimen at least 2 weeks before the first injection of study drug (i.e., Day 1 of Treatment Session 1). The short-acting anti-cholinergic medication for the treatment of sialorrhea may be continued throughout screening and study participation provided that the ALS subject agrees to hold the medication for at least 8 hours before the screening, baseline, and all subsequent study visits, so that the effectiveness and safety of the study drug can be properly evaluated.
 - Antihistamines and anticholinergic medications taken **for a non-sialorrhea condition** should be avoided as much as possible, but are not exclusionary.

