2.6.3 Other measures

Prior treatment for sialorrhea and concomitant medications (including those taken within 30 days before screening) taken over the course of the study will be recorded.

The medical history with disease history, co-morbidities, relevant past illness, and surgical procedures performed within the prior 6 months are recorded at screening. Subjects are also evaluated for presence or prior history of aspiration, aspiration pneumonia, choking, and/or dysphagia.

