3.2 Screening and Enrollment

An enrollment summary including the number of subjects enrolled (i.e., study participants), treated (i.e., safety population), efficacy evaluable (i.e., ITT population), and completed the study will be presented by site. Study participants include all individuals who have all required baseline (before injection of study medication) assessments/procedures completed at Day 1 visit. The number of subjects who received treatment doses will be summarized by session for safety population and for ITT population.

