5.14 Concomitant Medication

Concomitant medications were grouped into those taken pre-enrollment and those taken post-enrollment, based upon the starting date of both the concomitant medication and the enrollment date. Number and percent of subjects who take concomitant medications are reported for each Treatment Session. Concomitant medications will be listed, respectively, for individual subjects.

Solstice Neurosciences, LLC
SAP SN-SIAL-351

CONFIDENTIAL

22Jul2018
Page 28 of 36

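### Concomitant medications are sorted by start date alone against an undefined enrollment date, so drugs continued on treatment share a label with drugs stopped before Day 1

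*SAP*

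**What the plan says.** SAP 2.9.3, and SAP 5.14 in the same words, state that concomitant medications are "grouped into those taken pre-enrollment and those taken post-enrollment, based upon the starting date of both the concomitant medication and the enrollment date". Two outputs follow. One is a count by session: "Number and percent of subjects who take concomitant medications were reported for each Treatment Session" (5.14 has the same sentence in the present tense). The other is a listing: "Concomitant medications will be listed, respectively, for individual subjects".

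On what is collected, SAP 2.6.3 says that "concomitant medications (including those taken within 30 days before screening) taken over the course of the study will be recorded". SAP 2.6 names concomitant medications among the means by which safety is assessed.

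On enrollment, SAP 3.2 plans a summary of the "number of subjects enrolled (i.e., study participants), treated (i.e., safety population" and so on, and adds: "Study participants include all individuals who have all required baseline (before injection of study medication) assessments/procedures completed at Day 1 visit". That describes enrolled subjects and gives no date. Protocol 16.2.1, on intercurrent illness, pairs enrollment with screening as a point that precedes dosing.

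Protocol 11.1.2, criterion 9, bars antihistamines and anticholinergics for sialorrhea in most subjects, who must come off them in the 30 days before screening. ALS subjects may use a short-acting product, which "is required at a stable dose/regimen at least 2 weeks before the first injection of study drug", and may stay on it through the study. The same classes taken for other conditions are discouraged but allowed in anyone.

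**The concern.** The two groups are described as medications taken before or after enrollment, but the sorting variable is when the drug was started. For a continuing drug these differ: it was taken in both periods and gets only the earlier label. A reader of the table would take pre-enrollment to mean prior medication and could not tell a drug that was washed out from one used throughout treatment.

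This matters most for the drugs that the protocol itself singles out. Protocol 16.10 restricts anticholinergics and antihistamines because they can confound sialorrhea results. There is one arm, so no control group carries the same background medication. The 8-hour hold for ALS subjects covers clinic visits only. The subject's DFSS is a home diary, DFSS-I and DIS look back over the time since the previous visit, and adverse events accrue continuously. Dry mouth and dysphagia are both on the distant-spread list in SAP 5.6. Readers of the safety tables need to see who was using drying drugs during treatment.

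**Working it through.** The plan states no figure to reproduce. The check applies the written rule to typical cases under the two readings of enrollment date that the documents allow.

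**Inputs**
- Rule: compare medication start date with enrollment date (SAP 2.9.3, 5.14).
- Reading A: enrollment is Day 1 (inferred from SAP 3.2).
- Reading B: enrollment is consent or screening, up to 21 days before Day 1 (Protocol 16.2.1 for the usage, 14.2 for the window).
- A permitted ALS regimen is in place at least 14 days before Day 1 (Protocol 11.1.2, criterion 9).

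**Arithmetic.** Latest start of a permitted ALS regimen: Day 1 minus 14 days. Earliest consent: Day 1 minus 21 days. Interval in which a conversion can begin after consent and still be in time: 21 − 14 = 7 days. Protocol 16.10 asks that eligibility still hold after conversion, which suggests that conversion during screening was foreseen.

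**Cases**

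| Drug history | Taken on treatment? | Label, reading A | Label, reading B |
|---|---|---|---|
| Antisialorrhea drug stopped before screening (non-ALS) | No | Pre | Pre |
| ALS antisialorrhea drug begun before consent, continued | Yes | Pre | Pre |
| Anticholinergic for another condition, begun before consent, continued | Yes | Pre | Pre |
| ALS conversion begun in the first 7 days of a 21-day screening, continued | Yes | Pre | Post |
| Any drug begun and stopped within screening | No | Pre | Post |
| Any drug begun after the first injection | Yes | Post | Post |

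**Reading the table**
1. Rows 1 and 2 carry the same label under both readings, although one drug was washed out and the other continues. This part does not depend on how enrollment is defined.
2. Under reading A, every permitted ALS antisialorrhea drug is labelled pre-enrollment, because its start is at least 14 days before the reference date.
3. Under reading B that is no longer universal (row 4), and the opposite error appears: a drug never taken on treatment is labelled post-enrollment (row 5).
4. The per-session count is a separate output. An overlap rule would show rows 2 to 4 in each session of use; a start-date rule would omit them from every session. The SAP states neither, so two programmers could produce different tables from the same data.

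**The case against.** The strongest reply is that the pre/post grouping is not the only output. The next sentence counts subjects who take medications in each session, and that verb points to use, not initiation. A subject-level listing follows. A reader might infer from the start-date rule that the tables would show almost no background medication during treatment, and so would support a claim that response and adverse events arose without confounding drugs. The documents do not support that. They apply start date only to the pre/post grouping, they make no such claim, and a missing session rule is an ambiguity, not evidence that continuing drugs are dropped.

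A reader might also infer that every drug begun before Day 1, or every permitted ALS drug, is mislabelled. That requires enrollment to mean Day 1. SAP 3.2 supports this, but Protocol 16.2.1 points the other way.

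Finally, effectiveness is analysed as within-subject change from each pre-injection visit. A stable drug already in use then affects both measurements and is a weak explanation for change, and ALS drugs are also held before visits. No effectiveness or safety analysis uses the grouping.

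These points stand, and they limit the consequence to descriptive reporting. They do not rescue the rule, which assigns a wrong label to continuing drugs under either reading. The listing lets a determined reader recover the facts but does not replace a summary. The SAP's table and listing shells are not in the text available, so it cannot be ruled out that a shell resolves the session question.

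**Conclusion.** The concern holds as a defect of classification and labelling. Drugs begun before enrollment and continued on treatment are grouped with drugs stopped before Day 1, whichever reading of enrollment is used. Under the Day 1 reading this includes all permitted ALS antisialorrhea drugs. Under the consent or screening reading it excludes ALS conversions begun in the first 7 days of a full 21-day screening. The documents give no counts of medication use, so the number of subjects affected cannot be stated.

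The consequence is a misleading descriptive table for something SAP 2.6 counts as a safety measure, and per-session counts that cannot be reproduced from the text. No test, estimate or adverse event rate changes. It should be corrected, but it does not threaten the study's conclusions.

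**What to change.** In SAP 2.9.3 and 5.14:
- Use the date of first injection as the reference, in place of the undefined enrollment date.
- Class a drug as prior only if it stopped before that date. Class it as concomitant if it was ongoing on that date or started on or after it. A flag for drugs started before and ongoing is optional but useful.
- Count a drug in every treatment session that its start-to-stop interval overlaps: start on or before session end, and stop on or after session start or still ongoing.
- Add a rule for partial or missing medication dates. The date imputation in SAP 2.8 covers adverse event start dates only.

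Separate rows for anticholinergics and antihistamines, split by whether they were taken for sialorrhea, would help but are a display choice.

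The cost is a few SAP sentences and reprogrammed tables, provided that the eCRF holds stop dates or an ongoing flag. The documents say that medications are recorded but do not say that these fields are. If they are not, the least that can be done without new data is to relabel the groups as started before and started on or after the reference date, so that the heading matches the rule.
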